3.3. Tertiary objectives

- To evaluate the effect of the investigational vaccine on the presence, acquisition/apparition and load of NTHi and/or Mcat at stable visits and AECOPD by PCR.
- To evaluate the effect of the investigational vaccine on the presence, acquisition/apparition and load of NTHi and/or Mcat at stable visits and AECOPD in a subset of sputum samples by culture.
- To explore the efficacy of the investigational vaccine as compared to placebo with respect to the rate of all AECOPDs and by severity (i.e. mild, moderate or severe) associated with NTHi and/or Mcat detected in a subset of sputum samples by culture.
- To explore the impact of the investigational vaccine on health-related quality of life (HRQOL).
- To explore the impact of the investigational vaccine on use of medication for COPD and Healthcare Resource Utilisation.
- To explore the impact of the investigational vaccine on lung function.
- To describe selected biomarkers in stable COPD and during AECOPD.
- To explore the T helper profile of the PD-, PE-, PilA-, UspA2-specific CD4⁺/ CD8⁺ T cell responses.

CONFIDENTIAL

207489 (NTHI MCAT-002)

Statistical Analysis Plan Amendment 2 FDA Final Draft

- To collect blood and sputum samples for assay development, for lung microbiome analysis, to explore the level of inflammation (into the lung) and/ or for additional evaluation of the immune responses to the investigational vaccine and to other potential pathogens involved in AECOPD.
- To explore the data for an immune correlate of protection.

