6.3.1.1. Efficacy – Clinical Endpoints**6.3.1.1.1. Primary Analyses**

The primary analysis method of the vaccine VE will consider the exact inference on the risk ratio (R_{vacc} / R_{con}) based the total number of moderate and severe AECOPD observed in 1 year time of follow up.

VE is defined as: $VE = 1 - R_{vacc} / R_{con}$

being

- R_{vacc} = average yearly incidence rate of AECOPD events per subject in the group 10-10-3-AS.
- R_{con} = average yearly incidence rate of AECOPD events per subject in the placebo group.

Inferential statistic

Incidence rates and VE with 87% and 95% CIs will be tabulated for primary efficacy endpoint. P-value (to test $H_0 = [VE=0]$) will be tabulated for the primary endpoint.

The efficacy of vaccine in preventing moderate and severe AECOPD will be demonstrated if the lower limit of the two-sided 87% CI of VE is above 0.

The primary outcome will be analysed using the Negative Binomial regression model with number of AECOPD as dependent variable; treatment (vaccine or placebo), age group (40 - 59 yrs or 60 - 80 yrs), GOLD grade (2, 3 or 4) and history of moderate and severe exacerbations (<2 or ≥ 2) and country as independent variables, with logarithm as link function, and the logarithm of time for follow-up (in days) as an offset variable.

The following SAS code will be applied for primary analysis:

```
PROC GENMOD data=<dataset>;
  CLASS trt age gold hexac country;
  MODEL nb_exac = trt age gold hexac country
    / dist=NegBin LINK=log OFFSET=logfu alpha=0.13;
RUN;
```

Where

trt= treatment arm;
 age= Age Group;
 nb_exac=number of exacerbations;
 gold= GOLD grade at enrolment;
 hexac= History of moderate/severe exacerbation;
 country=Subject Country;
 fu= follow up time in days;
 logfu= log(fu);

CONFIDENTIAL

207489 (NTHI MCAT-002)

Statistical Analysis Plan Amendment 2 FDA Final Draft

Point estimate and CIs of the incidence rate for each arm, will be computed using a simple Negative Binomial model, without covariates and thus the following SAS code will be applied:

```

PROC GENMOD data=<dataset>;
BY trt;
MODEL nb_exac =           / dist =NegBin LINK=LOG OFFSET=LOGFU alpha=0.05;
ODS OUTPUT ParameterEstimates=out_parm NObs=Nobs;
RUN;

DATA parm_est(keep= val rate rate_LL rate_UL);
SET out_parm(WHERE=(Parameter='Intercept'));
format rate rate_LL rate_UL 8.2;
val= "Yearly Rate from Negative Binomial";
rate=EXP(Estimate)*365;
rate_LL=EXP(LowerWaldCL)*365;
rate_UL=EXP(UpperWaldCL)*365;
RUN;

```

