6.6.2. Health related quality of life (QOL)

The following analysis are exploratory and a p-value <0.1 will be considered statistically significant, however 2-sided 95% CIs will be computed to show precision of estimation. All comparisons should be interpreted with caution considering that there will be no adjustment for multiplicity.

For each of the following questionnaire missing items will not be imputed and subjects with partial data will be excluded.

EXACT-PRO daily score

The EXAcerbations of Chronic pulmonary disease Tool (EXACT) constitutes of 14 items which are patient-reported outcome (PRO) via daily diary.

All EXACT-pro scores will be divided in to the following periods:

- Screening: scores collected between screening and Visit 1 (Baseline)
- Treatment: scores collected between Visit 1 and Visit 4 (i.e., 1 month post-Dose 2)
- Exacerbation: scores collected during the start date of an exacerbation until resolution.
- Follow –up: scores collected between Visit 4 (1 month post-Dose 2) until study completion (one year after - Visit 8).
- Follow-up will be also divided by 3 months sub period:
 - from Visit 4 to Visit 5 (Day 91 to Day 180)
 - from Visit 5 to Visit 6 (Day 181 to Day 270)

CONFIDENTIAL

207489 (NTHI MCAT-002)

Statistical Analysis Plan Amendment 2 FDA Final Draft

- from Visit 6 to Visit 7 (Day 271 to Day 360)
- from Visit 7 to Visit 8 (Day 361 to Day 450)

Descriptive statistics

For each subject the average score across all days, within each period is computed. The mean score will be reported as descriptive statistics within each group (i.e., vaccine and placebo). N, mean, SD, median, min and max, on the **EXACT-PRO** average scores will be tabulated during all (stable) periods and during exacerbations.

Between groups comparison

At each period and sub period the two groups will be compared using an ANCOVA model, with the baseline value (i.e., score at screening) as covariate and treatment as fixed factor.

Note: EXACT-PRO baseline score at screening will be computed as the average within-patient score collected between screening Visit and Visit 1. If fewer than 4 days scores are available, the EXACT-PRO baseline score cannot be calculated, and it will result as missing.

COPD Assessment Test (CAT)

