A “Total” score is also computed as sum from all component items score, thus providing a global estimation of the patients respiratory health. Each of these scores ranges from 0 to 100, a score of 100 indicating maximum disability [Jones, 1991]

SGRQ-C will be provided to all enrolled patients at Screening, Day 271 and Day 451 (end of study), and at each exacerbation visit.

Descriptive statistics

Descriptive statistics (N, mean, SD, median, Q1, Q3, min and max) on the SGRQ-C (total score and symptoms, activity and impacts component scores) will be reported by scheduled visits (stable visits), at each AECOPD visit and by each treatment group.

Mean score for each component (symptoms, activity and impacts) and mean total scores will be also represented via line-chart at each time points (screening, Day 271, Day 415 and any AECOPD visit) together with the 95% confidence interval around the mean.

Within group change and SGRQ-C responders.

For each group and at each time point (Screening, Day 271 and Day 421), the mean of each component score and the mean of total score together with SD will be reported and a pair t-test will be performed to compare screening scores with scores at Day 271 and at Day 421. Moreover, the percentage of “SGRQ-C responder” subjects will be calculated at Day 271 and 421. A “SGRQ-C responder” is defined as a subject with an improvement of more than 4 unit (Decrease in total score) with respect to the baseline (Screening).

CONFIDENTIAL207489 (NTHI MCAT-002)
Statistical Analysis Plan Amendment 2 FDA Final Draft**Between groups comparison**

For all components and for the total scores, differences between groups will be analysed in terms of difference in mean for each time points (Day 271 and Day 421) by one-way ANOVA model on the total scores, with vaccine group as factor.

SGRQ-C at AECOPD Visit

N, mean, SD, median, min and max, of each component scores and of total score during AECOPD visit will be displayed according to the number and severity of AECOPD event.

Use of medication to treat (AE)COPD and Healthcare utilization (HCU)

Frequency table on the number and type of healthcare utilisation (Physician's office, Visit to Urgent Care, Visit to Emergency Department, Hospitalization) during entire study period will be presented overall and by vaccine group.

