Same frequency table will be also presented for two sub-periods: all HCU before 1-month after second vaccination and all HCU between 1-month after second vaccination and study end.

Frequency table on the use of medication for COPD (or AECOPD) and type (Chronic use for COPD, Chronic use for other disorders, exacerbation rescue medication) during entire study period will be presented overall and by vaccine group.

Medications will be coded using the GSKDRUG dictionary and frequencies table by GSKDRUG code will be also reported for entire study period, overall and by vaccine group.

As for HCU frequency tables will be presented also for the two sub-periods: before 1-month after second vaccination and after 1-month after second (until study completion).

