*** number of subjects who have been hospitalized consequently to an exacerbation

**** number of subjects who have been admitted to intensive care consequently to an exacerbation

% = based on total number of subjects and not subjects in each category

Template 43 Pulmonary function test by Visit

Visit		Screening		Day 271		Day 451	
Spirometer Parameter		10-10-3-AS N=	PLACEBO N=	10-10-3-AS N=	PLACEBO N=	10-10-3-AS N=	PLACEBO N=
FEV1 (L)	n						
	Mean						
	SD						
	Median						
	Minimum						
	Maximum						
FEV1 (% of predicted)	n						
	Mean						
	SD						
	Median						
	Minimum						
	Maximum						
FVC (L)	n						
	Mean						
	SD						
	Median						
	Minimum						
	Maximum						
FVC (% of predicted)	n						
	Mean						
	SD						
	Median						
	Minimum						
	Maximum						
FEV1/FVC	n						
	Mean						
	SD						
	Median						
	Minimum						
	Maximum						
PEF(L/sec)	n						
	Mean						
	SD						
	Median						
	Minimum						
	Maximum						
FEF25-75%	n						
	Mean						
	SD						
	Median						
	Minimum						
	Maximum						
FEF25-75% (% of predicted)	n						
	Mean						
	SD						
	Median						
	Minimum						
	Maximum						

<group description >

n = number of subjects in a given category; SD = Standard deviation,

FEV1 = Forced Expiratory Volume of air in 1 second (L), FVC = Forced Expiratory Vital Capacity (L), PEF= Peak Expiratory Flow (L/sec), FEF25-75% = Forced expiratory flow between 25% and 75% of FVC (L/sec)

Template 44 Descriptive statistics of biomarker

		10-10-3-AS N=	PLACEBO N=
Fibrinogen			
Day 1	Mean		
	SD		
	Minimum		
	Q1		
	Median		
	Q3		
	Maximum		
Day 451	Mean		
	SD		
	Minimum		
	Q1		
	Median		
	Q3		
	Maximum		
AECOPD Visit 1	Mean		
	SD		
	Minimum		
	Q1		
	Median		
	Q3		
	Maximum		
AECOPD Visit 2	Mean		
	SD		
	Minimum		
	Q1		
	Median		
	Q3		
	Maximum		
AECOPD Visit x	Mean		
	SD		
	Minimum		
	Q1		
	Median		
	Q3		
	Maximum		
hsCRP			
Day 1	Mean		
	SD		
	Minimum		
	Q1		
	Median		
	Q3		
	Maximum		
Day 451	Mean		
	SD		
	Minimum		
	Q1		
	Median		
	Q3		
	Maximum		

CONFIDENTIAL207489 (NTHI MCAT-002)
Statistical Analysis Plan Amendment 1 Final

		10-10-3-AS N=	PLACEBO N=
AECOPD Visit 1	Mean		
	SD		
	Minimum		
	Q1		
	Median		
	Q3		
	Maximum		
AECOPD Visit 2	Mean		
	SD		
	Minimum		
	Q1		
	Median		
	Q3		
	Maximum		
AECOPD Visit x	Mean		
	SD		
	Minimum		
	Q1		
	Median		
	Q3		
	Maximum		
IP-10.			
Day 1	Mean		
	SD		
	Minimum		
	Q1		
	Median		
	Q3		
	Maximum		
Day 451	Mean		
	SD		
	Minimum		
	Q1		
	Median		
	Q3		
	Maximum		
AECOPD Visit 1	Mean		

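### Healthcare contacts accumulate with follow-up, but the plan tabulates them by arm with no person-time and no between-arm estimate (low priority, tertiary objective)

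*SAP*

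**What the plan says.** The objective, in SAP section 3.3, is "To explore the impact of the investigational vaccine on use of medication for COPD and Healthcare Resource Utilisation".

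Section 6.6.2 meets it with tables only. For healthcare utilisation (HCU) it plans a "Frequency table on the number and type of healthcare utilisation", covering physician's office, urgent care, emergency department and hospitalisation, which "during entire study period will be presented overall and by vaccine group". It adds: "Same frequency table will be also presented for two sub-periods", split at 1 month after the second vaccination. Medication is handled the same way, with a "Frequency table on the use of medication for COPD (or AECOPD) and type" and a further table by drug code.

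The opening of section 6.6.2 says of the analyses that follow that "a p-value <0.1 will be considered statistically significant, however 2-sided 95% CIs will be computed to show precision of estimation". EXACT-PRO, CAT and SGRQ-C then each receive a named between-group model. HCU and medication receive none.

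For exacerbation counts, section 6.3.1.1.1 fits a negative binomial model with "the logarithm of time for follow-up (in days) as an offset variable" and tabulates total exposure time by arm. Section 11.1 scales the descriptive exacerbation rates of withdrawn subjects to the days they were observed.

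**The concern.** A healthcare contact can be counted only while the subject is under observation. In a table of subjects by number of contacts, someone who leaves after a month with none is indistinguishable from someone followed for a year with none. If one arm loses more follow-up, its distribution shifts towards fewer contacts without any vaccine effect, and the table does not show it.

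The second gap does not depend on withdrawal. The objective concerns the vaccine's impact and the section announces intervals, but for HCU no quantity is defined to which an interval could attach. The reader gets two columns of frequencies and must judge the difference and its precision by eye.

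At stake is how a tertiary result in an annex report is read. No primary or secondary conclusion depends on it.

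**Working it through.** The SAP states no figure for HCU, so there is none to reproduce.

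**Inputs from the SAP.** About 300 subjects per arm; follow-up from Day 1 to Day 451, so 450 days or 450/365.25 = 1.232 years (section 2).

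**Assumed inputs.** Equal true contact rates in both arms; 10% withdrawal in one arm and 15% to 25% in the other, with 30% as an outer case; withdrawals spread evenly over follow-up, so that a withdrawn subject contributes half the time on average; withdrawal unrelated to care use.

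**Step 1: size of the distortion.** Observed time per subject is proportional to 1 − w/2, where w is the proportion withdrawn. With equal true rates, the ratio of raw counts is (1 − w₂/2)/(1 − w₁/2). With w₁ = 0.10 and an illustrative rate of 1.0 contact per person-year:

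| Withdrawn, second vs first arm | Ratio of raw counts | Expected contacts per 300 subjects |
|---|---|---|
| 10% vs 10% | 1.000 | 351 vs 351 |
| 15% vs 10% | 0.925/0.95 = 0.974 | 342 vs 351 |
| 20% vs 10% | 0.900/0.95 = 0.947 | 333 vs 351 |
| 25% vs 10% | 0.875/0.95 = 0.921 | 323 vs 351 |
| 30% vs 10% | 0.850/0.95 = 0.895 | 314 vs 351 |

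For 15% to 25%, the apparent reduction is 2.6% to 7.9%. The ratio does not depend on the contact rate. With follow-up time as denominator it is 1.00 in every row.

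The percentage of subjects with at least one contact moves the same way. At 20% vs 10% withdrawn it is 65.2% vs 68.0% for Poisson counts, and 51.1% vs 53.2% for negative binomial counts with dispersion 1.

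**Step 2: would an estimate be informative?** For one year per subject, rate r and dispersion k, SE(log rate ratio) = √[2 × (1/(300r) + k/300)], and the 95% CI spans the estimate divided and multiplied by exp(1.96 × SE).

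- r = 1.5, k = 1: SE = √0.01111 = 0.105, factor 1.23.
- r = 3, k = 1: SE = √0.00889 = 0.094, factor 1.20.
- r = 0.3, k = 2 (a rarer type such as hospitalisation): SE = √0.03556 = 0.189, factor 1.45.

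The rates and dispersions are assumed. On these values total contacts would support a usable exploratory estimate; rare types would be much less precise.

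**Step 3: which care is already covered.** Section 11.2.4 grades exacerbations by the care they need: moderate by oral steroid or antibiotic treatment, severe by hospital admission or home care. Their combined rate is the primary endpoint, modelled with the follow-up offset. Section 6.3.1.1.2 adds incidence rates and vaccine efficacy with 95% CIs by severity. What remains without a follow-up-based estimate is mainly office, urgent-care and emergency contacts, and care outside those endpoints.

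**The case against.** The case for leaving the plan alone is substantial.

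- **Most exacerbation care is already estimated.** Step 3 bears this out. A reader might infer that the SAP adjusts exacerbations for follow-up but ignores the care they cause. The severity definitions do not support that reading.
- **Exposure by arm is printed elsewhere.** Section 6.3.1.1.1 tabulates exposure days by group with the same split at 1 month post-Dose 2, and section 6.1.1 tabulates withdrawals by group. A careful reader could form crude rates. This stands in part: section 6.6.2 names no analysis set for HCU, so the exposure may belong to different subjects, and crude division gives no interval.
- **Medication is not simply a recurrent count.** Chronic COPD treatment does not build up with follow-up, and frequencies suit it. This stands.
- **The distortion is conditional and small.** It needs unequal withdrawal, and at 3% to 8% it lies inside the sampling error of step 2. This also stands, but the planned tables show neither the distortion nor the sampling error.
- **Descriptive reporting is legitimate here.** The objective is exploratory, section 8 places it in an annex report, and lung function has similar wording and is also only described. But lung function is measured at fixed visits, where the number of subjects is a proper denominator; contacts depend on time observed.

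**Conclusion.** The point holds in limited form. For healthcare contacts the plan gives by-arm frequencies with no person-time and no between-arm estimate or interval, although section 6.6.2 announces intervals and the SAP accounts for follow-up when it counts exacerbations. Under the assumed withdrawal of 10% vs 15% to 25%, the arm with less follow-up would show about 3% to 8% fewer contacts at equal true rates. With equal withdrawal this distortion disappears, but effect size and precision are still not reported.

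Two stronger readings are not supported. One is that the tables will mislead: the SAP states no withdrawal rate, and either arm could lose more follow-up. The other is that the objective cannot be addressed at all: arm-level frequencies are shown, and the moderate and severe endpoints cover much of the care of interest.

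The only HCU layout in the file, Template 42 in section 13.2 of SAP Amendment 1, has percentages "based on total number of subjects and not subjects in each category". It belongs to a superseded version, so it only illustrates how subjects already withdrawn could enter the later sub-period as zero use. The current text does not rule this out.

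Priority is low: the objective is tertiary and the primary conclusion is not affected.

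**What to change.** In section 6.6.2:

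1. Keep the HCU and medication frequency tables. Chronic COPD medication needs nothing more.
2. Name the analysis set, and print the number of subjects at risk and the person-time by arm in each HCU table: whole study and both sub-periods.
3. For the period from 1 month post-Dose 2, report contacts per person-year by arm and one rate ratio with 95% CI for total HCU contacts. Use the section 6.3.1.1.1 negative binomial model with its covariates and log follow-up offset, setting alpha to 0.05 in place of the 0.13 in that code. Label it exploratory.
4. Repeat by contact type only where counts allow; otherwise give rates alone.
5. State what counts as one contact. Section 11.2 gives no rule, although the planned sub-period split already requires contacts to be dated.

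The cost is SAP wording, a derivation rule and a few runs of existing code. The downside is a few more unadjusted exploratory estimates, which the cautions in sections 6.6.2 and 7 already cover. The offset removes the distortion only if withdrawal is unrelated to care use, and the report should say so.

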6.6.3. Lung function and biomarkers**Pre- and post-bronchodilator spirometry**

Pre- and post-bronchodilator spirometry assessments will be done at the Screening Visit (pre Day 1), Visit 6 (Day 271) and at Visit 8 (Day 451).

The following pulmonary function parameters will be evaluated:

- Forced Expiratory Volume in 1 second (L): **FEV₁**
- Forced Expiratory Volume in 1 second percent of predicted (%): **FEV₁PP**
- Forced Vital Capacity (L): **FVC**
- Forced Vital Capacity percent of predicted (%): **FVCPP**
- FEV₁ and FVC ratio: **FEV₁/FVC**

CONFIDENTIAL

207489 (NTHI MCAT-002)
 Statistical Analysis Plan Amendment 2 FDA Final Draft

- Peak Expiratory Flow (L/sec): **PEF**
- Forced expiratory flow between 25% and 75% of FVC (L/sec): **FEF_{25-75%}**
- FEF between 25-75% of FVC percent of predicted(%): **FEF_{25-75%PP}**

Descriptive analysis (N, mean, SD, median, min and max) on all spirometric measurements at each time point.

Biomarkers

The following selected biomarkers will be evaluated at Day 1 and Day 451 and at each AECOPD visit: fibrinogen, hsCRP and IP-10.

Descriptive statistics (N, mean, SD, median, min and max) will be tabulated for each biomarker and at each time point.

6.6.4. Correlate of protection

An exploratory analysis will be implemented in an attempt to correlate humoral immune responses to vaccination and efficacy (i.e., reduction in AECOPD). Details of the methodologies will be included in ad hoc SAP for this purpose.

7. ANALYSIS INTERPRETATION

The primary objective analysis (efficacy) of this study will be evaluated at alpha error of 13% (two-sided test) which is the measurement of the accuracy of our estimation.

Also 2-sided 95% CIs will be provided to show the precision of estimation.

For the secondary objectives we have the following:

- Inferential analyses for primary analysis of efficacy are planned to be performed at alpha level of 0.13 (two sided). No alpha adjustment for multiple testing in the secondary endpoints will be performed, and only the 2-sided 95% CIs will be provided
- All other efficacy and immunogenicity analyses are planned to be performed at alpha level of 0.05 with no adjustment for multiplicity.

CMI and safety analyses are intended to be descriptively only.

All tertiary objectives are exploratory and a p-value <0.1 is considered as reference for statistical significance in comparative analysis. Those comparisons should be interpreted with caution.

CONFIDENTIAL

207489 (NTHI MCAT-002)

Statistical Analysis Plan Amendment 2 FDA Final Draft

8. CONDUCT OF ANALYSES

The analysis planned in this study will be performed in four steps giving higher priority to the most relevant objectives (i.e., primary, secondary)

Specifically, the analyses will be released in this order:

- Priority 1 analyses will be released at first and reported in a full clinical study report (CSR), this analysis is performed in to two steps:
 - Step 1: Analysis of primary efficacy endpoint and secondary safety endpoint.
 - Step 2: Analysis of immunogenicity, CMI and bacteriological PCR secondary endpoints plus the following tertiary objectives:
 - To evaluate the effect of the investigational vaccine on the presence and load of NTHi and/or Mcat at stable visits and AECOPD by PCR.
 - To explore the impact of the investigational vaccine on health-related quality of life (HRQOL).
 - To explore the T helper profile of the PD-, PE-, PilA-, UspA2-specific CD4+/ CD8+ T cell responses
- Priority 2 analysis will be released in a third step and reported in to an Annex report. They include, the following tertiary objectives:
 - *To evaluate the effect of the investigational vaccine on the presence, acquisition/apparition and load of NTHi and/or Mcat at stable visits and AECOPD by culture.*
 - *To evaluate the effect of the investigational vaccine on the presence, acquisition/apparition and load of NTHi and/or Mcat at stable visits and AECOPD by culture. To explore the efficacy of the investigational vaccine as compared to placebo with respect to the rate of all AECOPDs and by severity (i.e. mild, moderate or severe) associated with NTHi and/or Mcat detected in a subset of sputum samples by culture.*
 - *To explore the impact of the investigational vaccine on use of medication for COPD and Healthcare Resource Utilization.*
 - *To explore the impact of the investigational vaccine on lung function.*
 - *To describe selected biomarkers in stable COPD and during AECOPD*

and other stratified analyses to evaluate VE in subsets:

- Vaccine efficacy (clinical and bacteriological) by eosinophil level in blood at baseline
- Vaccine efficacy (clinical and bacteriological) by NTHi presence in sputum (detected by PCR) at baseline
- Vaccine efficacy (clinical and bacteriological) by Mcat presence in sputum (detected by PCR) at baseline

CONFIDENTIAL

207489 (NTHI MCAT-002)

Statistical Analysis Plan Amendment 2 FDA Final Draft

- Vaccine efficacy (clinical and bacteriological) by NTHi or Mcat presence in sputum (detected by PCR) at baseline
- Priority 3, analyses will be release in a fourth step and reported in an Annex or technical report (if related to assay development) and they include the following tertiary objectives:
 - *To collect blood and sputum samples for assay development, for lung microbiome analysis, to explore the level of inflammation (into the lung) and/ or for additional evaluation of the immune responses to the investigational vaccine and to other potential pathogens involved in AECOPD.*
 - *To explore the data for an immune correlate of protection*

And additional request for EXACT event analysis

In addition to the data and analysis for the clinical study report, four safety interim data evaluations will be carried by an internal Safety Review Committee (iSRC).

